6.3.1. Safety Population

The Safety Population will consist of all subjects who have received the study vaccine and for whom any data on safety are available. Subjects will be classified according to the treatment received. The primary safety analysis will be done on this population.

6.3.2. Immunogenicity Population

The Immunogenicity Population will include all subjects who have received the study vaccination and contributed both pre-vaccination samples and either at least one post vaccination sample for humoral immunogenicity testing for which valid results were reported, or at least one post vaccination nasal sample for which valid results were reported. Subjects will be classified according to the treatment received.

6.3.3. Per Protocol Population

The Per Protocol (PP) Population will include all subjects in the immunogenicity population, with the following exclusions:

-
- Data from all available visits for subjects found to be ineligible at baseline.
 - Data from all visits subsequent to major protocol deviations, such as:
 - Receipt of non-study licensed live vaccine within 30 days before or after the study vaccination,
 - Receipt of non-study licensed inactivated vaccine within 14 days before or after the study vaccination,
 - Receipt of immunosuppressive therapy (e.g., corticosteroids) within 30 days before or after the study vaccination.
 - Data from any visit that occurs substantially out of window. Whether a visit that occurs substantially out of window will be determined jointly by the principal investigator, the Sponsor, and the SDCC.

For analyses using the PP population, subjects will be grouped based on study vaccinations received.

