⁷ *Close contact includes sharing a household, serving as a healthcare worker, or working professionally in settings with repeated exposures.*

19. Receipt of *B. pertussis*-active antibiotics⁸ within 7 days prior to vaccination

⁸ *B. pertussis* active antibiotics include macrolides, fluoroquinolones, trimethoprim-sulfamethoxazole, tetracyclines

20. Known hypersensitivity to any component of the study vaccine.

21. Hypersensitivity to azithromycin, which may be used in the event of ongoing BPZE1 colonization

22. Any condition that, in the opinion of the investigator, might interfere with objectives of the study or safety to the individual

23. Acute illness, including temperature >100°F within one week prior to vaccination⁹

⁹ *Enrollment may be postponed if acute illness occurs; subjects must remain within the screening window, however, and must be rescreened if >30 days elapses prior to enrollment.*

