4.4.7. Prior and Concomitant Therapy

Administration of medications, therapies, or vaccines will be recorded on the appropriate data collection form. Concomitant medications will include all current medications and medications taken within 30 days prior to

signing the informed consent form through approximately 28 days after study vaccination (or through the early termination visit if prior to that time). Prescription and over-the-counter drugs will be included, as well as herbals, vitamins and supplements. In addition, receipt of non-study vaccines will be solicited through approximately 181 days after study vaccination and reported in the eCRF.

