7.2. Protocol Deviations

A summary of subject-specific protocol deviations will be presented by the deviation category, deviation type, and treatment group for all enrolled subjects ([Table 5](#).) Deviations that are considered major deviations that will be reviewed for possible subject exclusion from the per protocol population include: deviations related to eligibility/enrollment, treatment administration schedule, follow-up visit schedule, and study product or specimen temperature excursions. All subject-specific protocol deviations and non-subject specific protocol deviations will be included in [Appendix 3](#) as data listings ([Listing 2](#) and [Listing 3](#), respectively.)

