9.1.2. Prior and Concomitant Medications

During screening, medications and vaccines used up to 30 days prior will be solicited. Any medications used within 30 days prior to signing the informed consent form through 28 days after study vaccination (or early termination if prior to 28 days after study vaccination) will be recorded in the eCRFs. In addition, receipt of non-study vaccines will be solicited through approximately 28 days after study vaccination and recorded in the eCRFs.

Summaries of medications that were started prior to dosing and continuing at the time of dosing will be presented by WHO Drug Terms 2 and 3 and treatment group ([Table 80](#).)

Individual subject listings will be presented for all concomitant medications ([Listing 18](#).)

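### The per-protocol rules do not remove antibody results taken after a pertussis-containing vaccine given beyond about Day 28, and the SAP contradicts itself on how long such vaccines are recorded

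*SAP*

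**What the plan says.** SAP 6.3.3 and Protocol 11.4.1.3 carry the same PP list. After baseline ineligibility, they remove "Data from all visits subsequent to major protocol deviations, such as" three named examples. For live vaccines the span is 30 days either side of dosing. For inactivated vaccines the wording is "Receipt of non-study licensed inactivated vaccine within 14 days before or after the study vaccination". The third example is immunosuppressive treatment, with the same 30-day span as live vaccines. Visits substantially out of window are also removed. SAP 7.2 says which deviation types are reviewed for PP exclusion: "deviations related to eligibility/enrollment, treatment administration schedule, follow-up visit schedule, and study product or specimen temperature excursions".

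Protocol 5.2 bars a pertussis vaccine in the 2 years before entry, and bars subjects who plan any licensed vaccine within 28 days of dosing. It bars B. pertussis-active antibiotics in the 7 days before dosing; footnote 8 says that these "active antibiotics include macrolides, fluoroquinolones, trimethoprim-sulfamethoxazole, tetracyclines". Protocol 6.6 discourages interfering medication after dosing but allows it when clinically indicated.

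On recording, SAP 4.4.7 states that "receipt of non-study vaccines will be solicited through approximately 181 days after study vaccination and reported in the eCRF", as does Protocol 6.6. SAP 9.1.2 states that "receipt of non-study vaccines will be solicited through approximately 28 days after study vaccination and recorded in the eCRFs".

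Serum results are analysed in the Immunogenicity and PP populations (SAP 8.1). Nasal culture is summarised in the PP population only (SAP 6.3).

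**The concern.** The serum endpoints are IgG and IgA to PT, FHA, PRN and FIM 2/3, reported as GMT, fold rise and two-fold seroconversion at Days 15, 29 and 181, with seroconversion also at any time point. A pertussis-containing vaccine given between Day 29 and Day 181 can raise those same antibodies. Subjects enter with low PT and PRN IgG (Protocol 5.2, criterion 10), so a two-fold rise after such a vaccine is plausible. The Day 181 result would then reflect the other vaccine at least as much as the study product. Neither planned population is clear of such results.

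A related gap concerns antibiotics. In Phase 1a, IgG appeared only in colonised subjects. In Phase 1b, serum response was strongly correlated with colonisation (Protocol 2.1.1 and 2.1.2). An active antibiotic taken during colonisation could therefore shorten carriage or blunt response, and no planned summary separates those subjects.

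These are secondary outcomes, but Protocol 11.4 says the results will inform the dose for a Phase 2b study.

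**Working it through.** **1. Text check: what covers a pertussis vaccine, by time of receipt**

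| Days after dosing | Covering rule | Effect on later PP data |
|---|---|---|
| 0 to 14 | Listed PP deviation (inactivated) | Removed |
| 15 to 28 | Outside the inactivated-vaccine window; an eligibility breach if planned at entry | Removed only if ruled ineligible at baseline |
| 29 to 180 | None for an inactivated vaccine | Not removed |

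Taking Day 181 as 180 days after dosing, 180 − 14 = 166 days (92%) lie outside the listed inactivated-vaccine window, and 180 − 28 = 152 days (84%) lie beyond the 28-day eligibility rule as well. The Immunogenicity Population has no exclusion of this kind at any time.

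**2. Size in one arm**

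One subject whose status changes: 1/15 = 6.7 points. Two: 2/15 = 13.3 points. The condition is that the subject had not already converted.

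**3. The plan's own figure, reproduced**

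Table 4 (15 vs 15, two-sided Fisher's exact test, alpha 0.05, 80% power) was checked by enumerating two independent Binomial(15, p) arms and rejecting when p ≤ 0.05. Power at its five rows (placebo 0.00, 0.01, 0.05, 0.10, 0.20) is 0.805, 0.792, 0.805, 0.793 and 0.805. The table reproduces.

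**4. Illustration in the placebo arm**

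True rates are those of the first Table 4 row, 0.00 vs 0.41. The number of placebo subjects converted by a later vaccine is an assumption. Power is P(X ≥ m), with X ~ Binomial(15, 0.41) and m the smallest BPZE1 count reaching p ≤ 0.05.

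| Placebo conversions | m | Power |
|---|---|---|
| 0/15 | 5 | 80.5% |
| 1/15 | 7 | 42% |
| 2/15 | 9 | 11% |
| One affected subject removed (0/14 vs 15) | – | 80.5% |

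The SAP compares rates with Barnard's test, so cut-offs differ (1 vs 6 of 15: Fisher p = 0.080, Barnard p = 0.043). The direction does not: 5/15 gives Barnard p = 0.018 against 0/15 and 0.100 against 1/15.

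**5. Chance that it happens**

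The documents give no rate. With an assumed per-subject rate r, the chance of at least one case is 1 − (1 − r)^n.

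| r | n = 15 | n = 50 |
|---|---|---|
| 1% | 14% | 40% |
| 2% | 26% | 64% |
| 5% | 54% | 92% |
| 10% | 79% | 99.5% |

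**6. Recording passages side by side**

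- 181 days: SAP 4.4.7; Protocol 6.6, 7.4 and 8.1; Protocol Appendix A at Visit 5, with a non-study vaccine row at Visit 4a.
- 28 days: SAP 9.1.2. SAP Table 1 leaves the Visit 5 medication cell empty, and SAP Table 2 has no non-study vaccine row for Visit 4a.

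**7. Antibiotics**

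Concomitant medications are recorded to about 28 days after dosing, so use before the Day 29 sample can be identified. Phase 1 colonisation was first detected on days 4 to 14 and lasted to days 11 to 28. As an illustration, with an assumed 3 carriers in 15 at Day 29 the proportion is 20% (exact 95% CI 4% to 48%). If antibiotics cleared two of them it is 7% (0.2% to 32%).

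**The case against.** The PP list is open-ended, and any noncompliance with the protocol is a deviation (Protocol 15.6), so the study team could add an exclusion. That stands, and it rules out saying flatly that the rule keeps every such subject. But the clause reaches only protocol deviations. A pertussis vaccine after about Day 28, or a clinically indicated antibiotic, is not clearly one, so any exclusion would be ad hoc. The outlier rule in SAP 6.5 is for values that look erroneous or cannot be explained; a rise after a recorded vaccine is neither.

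In the BPZE1 arms the effect on conversion to one or more antigens may be small. In Phase 1b, more than 92% (10^7) and 100% (10^9) had a two-fold rise in at least one antibody, under a criterion with an added detection-limit threshold. That stands, and is why the placebo arm matters most. Individual-antigen conversion and Day 181 GMTs remain exposed in every arm.

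The trial tests no formal hypothesis, so the power figures show sensitivity to one subject and are not a predicted loss.

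A reader might infer that the later vaccine would go unrecorded. The documents do not support that: the protocol collects non-study vaccines to Day 181, and the SAP refers readers to the protocol for operational detail. The 28-day passages are inconsistencies in the SAP.

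A reader might also call a Day 29 culture after an antibiotic falsely negative. If the organism was cleared, the culture is truly negative; what is in doubt is the cause of clearance. Most earlier subjects were clear by Day 29 in any case (Protocol 2.3.1.2), so few results could change.

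**Conclusion.** The point holds in a limited form. The PP rules do not pre-specify what happens to antibody results after a pertussis-containing vaccine given beyond about Day 28, and as written those results stay in both immunogenicity populations. Each subject whose status changes moves a 15-subject arm by 6.7 points. That figure assumes the subject had not already converted and that the vaccine causes a two-fold rise. How often this would occur cannot be judged from the documents.

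The conflict within the SAP on vaccine capture is certain and needs correcting in any case.

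For antibiotics, a reader might infer that all later data should be excluded. The documents do not support so broad a rule. Use close to Day 29 may have no bearing on response, and respiratory symptoms could prompt treatment, so exclusion after randomisation could itself introduce selection. A sensitivity summary is enough. Extending the vaccine rule to wild-type pertussis is not workable either: the plan has no confirmation procedure, non-serious events are collected only to about 28 days, and any positive culture is attributed to the study product.

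**What to change.** 1. Add to SAP 6.3.3 and Protocol 11.4.1.3 that immunogenicity data collected after receipt of any non-study pertussis-containing vaccine, through Day 181, are excluded from the PP population. The Immunogenicity Population continues to show them, so the effect of the rule is visible.

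2. Reconcile SAP 9.1.2, SAP Table 1 (Visit 5) and SAP Table 2 (Visit 4a) with the 181-day non-study vaccine capture in SAP 4.4.7 and Protocol 6.6.

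3. For subjects with a recorded footnote-8 antibiotic between dosing and the Day 29 sample, keep the main summaries unchanged. Pre-specify one sensitivity table showing Day 29 culture and immunogenicity with and without these subjects, because clearance or non-response could be due to the antibiotic. Medication capture ends at about 28 days, so this cannot extend to the Day 46 culture, and the table should say so.

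The cost is wording in two documents, one extra table and possibly a few lost PP observations. No new data collection is needed.

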6.4. Covariates and Subgroups

The protocol does not define any formal subgroup analyses, and the study is not adequately powered to perform subgroup analyses.

6.5. Missing Data

All attempts will be made to collect all data per protocol. As missing data are expected to be minimal, no imputation will be performed for missing values. Any data point that appears to be erroneous or inexplicable based on clinical judgment will be investigated as a possible outlier. If data points are identified as outliers, sensitivity analyses will be performed to examine the impact of including or excluding the outliers. Any substantive differences in these analyses will be reported.

6.6. Interim Analyses and Data Monitoring

Interim analyses would only be used to terminate this trial in the event that unanticipated safety events deemed to be of sufficient concern require such action by the sponsor. These interim assessments will not be made based on testing a formal statistical hypothesis; therefore, p-value adjustment will not be made to any analyses.

6.6.1. Interim Safety Review

An ISM and SMC will be convened by DMID to review study progress and participant, clinical, safety, and reactogenicity data. An interim safety review may include enrollment and demographic information, medical history, concomitant medications, physical assessments, clinical laboratory values, dosing compliance, solicited and unsolicited AE/SAEs, and *B. pertussis* colonization data. Additional data may be requested by the SMC, and interim statistical reports may be generated as deemed necessary and appropriate by DMID. The SMC may receive data in aggregate and presented by treatment arm, including expected and observed rates of the expected AEs. The SMC will review grouped data in the closed session only. The SMC will meet and review this data at scheduled time points or ad hoc as needed during this trial as defined in the SMC charter. As an outcome of each review/meeting, the SMC will make a recommendation as to the advisability of proceeding with study vaccinations (as applicable), and to continue, modify, or terminate this trial.

Additionally, this trial will be monitored to determine if any of the halting rules described in Section 9.5 of the protocol are met.

A preliminary report prepared with data through Day 46 (or Day 29 if no subjects remain colonized with *B. pertussis* at the Day 29 visit) will be prepared. This report will include analyses of safety and immunogenicity data.

6.6.2. Interim Immunogenicity Review

A preliminary report of safety and immunogenicity and *B. pertussis* colonization data through Day 46 (or Day 29 if no subjects remain colonized with *B. pertussis* at the Day 29 visit) will be prepared. The analyses presented in this report will be released while subjects remain in the trial for long-term safety and immunogenicity follow-up and will be included in the final analysis of these data.

6.7. Multicenter Studies

Not applicable. This study will take place at a single VTEU site.

6.8. Multiple Comparisons/Multiplicity

This study was not designed to test any specific null hypothesis, and as such no adjustments for multiple testing are planned.

7. STUDY SUBJECTS

7.1. Disposition of Subjects

[Table 13](#) will present a summary of the reasons that subjects were screened but not enrolled.

The composition of analysis populations, including reasons for subject exclusion, by treatment arm, is presented in [Table 11](#). A listing of subjects excluded from each analysis population will be presented in [Listing 4](#).

The disposition of subjects in the study will be tabulated by treatment group ([Table 10](#)). The table shows the total number of subjects screened, enrolled, receiving study product, completing the Day 8 visit, completing the Day 15 reactogenicity period, completing the Day 29 blood draw, terminated from study follow-up, and the number who completed the study.

A flowchart showing the disposition of study subjects, adapted from the CONSORT Statement [15] will be included ([Figure 2](#)). This figure will present the number of subjects screened, enrolled, lost to follow-up, and analyzed, by treatment arm.

A listing of subjects who terminated from study follow-up and the reason will be included in [Listing 1](#).

7.2. Protocol Deviations

A summary of subject-specific protocol deviations will be presented by the deviation category, deviation type, and treatment group for all enrolled subjects ([Table 5](#).) Deviations that are considered major deviations that will be reviewed for possible subject exclusion from the per protocol population include: deviations related to eligibility/enrollment, treatment administration schedule, follow-up visit schedule, and study product or specimen temperature excursions. All subject-specific protocol deviations and non-subject specific protocol deviations will be included in [Appendix 3](#) as data listings ([Listing 2](#) and [Listing 3](#), respectively.)

8. EFFICACY EVALUATION

This study was not designed to test a specific null hypothesis, rather the primary objectives included assessing the safety and tolerability of lyophilized BPZE1 vaccine.

8.1. Secondary Immunogenicity Analysis

Summaries and analysis of immunogenicity data will be presented for the immunogenicity and PP populations by treatment group.

Immune responses in terms of toxin-specific serum IgG and IgA antibody titers (PT, FHA, PRN, FIM 2/3) will be summarized at each time point. Analyses will include the Geometric Mean Titers (GMTs) along with corresponding 95% confidence intervals (Table 17, Table 18, Table 19, and Table 20) and Geometric Mean Fold Rise (GMFR) (Table 21, Table 22, Table 23, and Table 24), as well as the proportion of subjects achieving seroconversion (defined as 2-fold increase over baseline of GMT) for each antigen (PT, FHA, PRN, and FIM 2/3) and the proportion of subjects that achieved seroconversion for ≥ 1 (Table 25 and Table 26) and ≥ 2 (Table 27 and Table 28) antigens (PT, FHA, PRN, and FIM 2/3.) Rates of seroconversion will be compared using Barnard's exact test. Reverse cumulative distributions (RCD) curves will also be presented for PT, FHA, PRN, and FIM 2/3 antibody titers. Plots for each assay will be generated with four panels (pre-vaccination, Day 15, Day 29, and Day 181), and separate curves within each panel for each treatment group, as shown in Figure 3, Figure 4, Figure 5, and Figure 6. Individual immunogenicity response data will also be presented (Listing 7 and Listing 8.)

Immune responses in terms of the ratio of toxin-specific (PT, FHA, PRN, FIM 2/3) nasal mucosal IgA antibody to total nasal mucosal IgA antibody will be summarized at each time point (Table 29 and Table 30.) Analyses will include the geometric mean titer ratios (GMTR) of antigen-specific IgA to total IgA and corresponding 95% confidence intervals, along with fold change of the GMTR from baseline. The proportion of subjects achieving seroconversion, defined as ≥ 2 -fold rise of the GMTR from baseline, to each antigen (PT, FHA, PRN, and FIM 2/3) will be reported (Table 29 and Table 30) as well as the proportion of subjects that achieve seroconversion by nasal aspirate ELISA to one or more (Table 31 and Table 32) antigens (PT, FHA, PRN, and FIM 2/3) at either or both of Day 29 and Day 181. Rates of seroconversion will be compared using Barnard's exact test. Reverse cumulative distributions (RCD) curves will also be presented for mucosal PT, FHA, PRN, and FIM 2/3 antibody titers. Plots for each assay will be generated with three panels (pre-vaccination, Day 15, Day 29, and Day 181), and separate curves within each panel for each treatment group, as shown in Figure 7 and Figure 8. Individual immunogenicity response data will also be presented (Listing 9.)

Subjects will be tested for *B. pertussis* colonization by culture at Day 29 and, if positive, again at Day 46. The proportion of subjects with positive *B. pertussis* culture will be reported for the PP population at each time point with corresponding 95% confidence intervals (Table 33.) Individual nasal colonization data will also be presented (Listing 13.)

No formal hypothesis testing is planned.

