2.1.2 Phase 1b Clinical Study Results

The BPZE1 investigational liquid vaccine was safe in the higher doses and volumes used for nasal administration. Proportion of subjects having transiently BPZE1 colonized nasopharyngeal mucosa was not dose-related at 10^7 CFU or higher, but instead all dosage groups achieving 75% colonization rate or greater, and an overall combined colonization rate was observed for subjects from all randomized groups of over 80%. A dose response trend was observed, however, in the rate of colonization and clearance, with faster colonization rate and faster clearance rate being correlated with higher dosage. The serum antibody responses were strongly correlated to positive colonization, but there was no dose response. A small non-randomized group of subjects with

pre-existing high antibody titers for pertactin had a 33% rate of BPZE1 colonization after immunization with the 10^9 CFU dose.

There were no SAEs and any differences in AEs within randomized study groups, between placebo and the different dosages, were not detectable. The most frequent AEs were sneezing (n=55 episodes in 24 subjects), rhinorrhea (n=35 episodes in 22 subjects), nasal congestion (n=31 episodes in 19 subjects), cough (n=21 episodes in 16 subjects), and fatigue (n=21 episodes in 16 subjects). Efficacy results, included:

- *Colonization of mucosal surface:* The vaccine strain BPZE1 was isolated in a total of 29 randomized subjects, 10 in the 10^7 CFU dose group, 9 in the 10^8 CFU dose group, and 10 subjects in the 10^9 CFU dose group. Colonization was first detected on day 4-14 and lasted through day 11-28 after vaccination.
- *Immunogenicity:* Serologic responses (IgG and IgA) were measured to PT, PRN, FIM, and FHA and reported individually. In addition, responses were grouped by either:
 - ≥ 2 -fold rise in PT-specific IgG or IgA that was at least 4x greater than the minimum limit of detection (MLD) of the assay, or
 - ≥ 2 -fold rise in at least 2 antibodies targeting PRN, FIM, or FHA (IgG or IgA) that were at least 4x greater than the MLD

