Greater than 92% of subjects in the 10^7 CFU dose group and 100% of subjects in the 10^9 CFU dose group had a two-fold rise in at least one antibody titer (either PT, PRN, FIM, or FHA, IgG or IgA) that was at least 4x greater than the MLD (i.e., seropositive). All subjects receiving the 10^9 CFU BPZE1 dose were seropositive for at least 2 or more antibodies (IgG or IgA) or PT (IgG or IgA). No placebo subjects had 2 seropositive antibodies (IgG or IgA) or seropositive for PT antibodies (IgG or IgA). In the vast majority of subjects, an increase in serum antibody titers (IgG/IgA) occurred at day 14 or 21, peaked at day 28, and remained at high levels at the 6 months follow up visit (sometimes rising further at 6-months).

- Despite 33% BPZE1 colonization rate in the non-randomized pre-existing high pertactin group, 66% of the subjects experienced a seropositive response to ≥ 2 antibodies (IgG or IgA) or PT (IgG or IgA); in other words, multiple subjects generated an immunological response despite unrecognized BPZE1 colonization.

In summary, the investigational BPZE1 liquid vaccine was safe in the doses used for nasal administration. Colonization occurred in $> 80\%$ of the subjects across the three dosage groups and BPZE1 groups, especially the 10^9 CFU group, had a high proportion of subjects that reached the pre-specified threshold of seropositivity. Additionally, subjects with high baseline antibodies were capable of further seropositive antibody boosting, but at a lower rate and lower percent increase from baseline.

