5.3.5 Subject Replacement

Subjects who withdraw, are withdrawn/terminated from this study, or are lost to follow-up after signing the informed consent form and randomization but before receipt of study vaccine may be replaced. Subjects who are vaccinated, but do not complete the Day 15 visit, will be replaced. Subjects who are vaccinated and subsequently, after the Day 15 visit, withdraw, are withdrawn or terminated from this study, or are lost to follow-up will not be replaced. Subjects who were previously screened and found to be ineligible due to initial serum concentrations of PRN IgG \geq 20 IU/ml in protocol version 3.0 may be rescreened per the revised exclusion criterion of protocol version 4.0.

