11.2 Sample Size Considerations

The study population for this clinical trial includes healthy male and non-pregnant female subjects 18-49 years of age, inclusive, who meet all eligibility criteria. Study subjects will be recruited from the general population at the Vanderbilt University Medical Center VTEU site. This study is planned to enroll approximately 50 healthy adults randomized into four treatment groups in a 3:3:3:1 ratio, as described in [Table 2 \(Section 4\)](#). The tables below describe the probability of observing safety events and the minimum detectable difference in seroconversion rates for the planned sample size.

[Table 3](#) indicates the probability of observing one or more safety events (such as solicited local or systemic reactogenicity events, or an unsolicited non-serious AE of a particular type) for a treatment arm with the assumed event frequency and for the given sample size. For example, for any of the treatment arms with a sample size of 15 subjects, there is a 79.4% probability of detecting an AE that occurs at a frequency of 10%, and a 14% probability if the AE occurs at a rate of 1%.

Table 3: Probability (%) of Observing at Least One Adverse Event

| Event Frequency | N = 5 | N=15 |
|------------------------|--------------|-------------|
| ≥0.01% Rare | <0.1 | <0.1 |
| ≥0.1% Uncommon | 0.5 | 1.5 |
| ≥1% Common | 4.9 | 14.0 |
| ≥10% Very Common | 41.0 | 79.4 |

One of the secondary outcome measures is the proportion of subjects that achieve seroconversion to individual pertussis antigens (PT, FHA, PRN, and FIM 2/3) by serum IgG or IgA ELISA at Days 15, 29 and 181 for humoral immune response. Table 4 shows the minimum detectable differences with 80% power between the proportion of subjects attaining seroconversion in the BPZE1 by VaxINator group versus Placebo using a two-sided Fisher’s Exact test and alpha = 0.05.

Table 4: Minimum Detectable Difference in Proportion of Subjects Attaining Seroconversion comparing Placebo versus the BPZE1 (107 or 109 CFU)

| Placebo by VaxINator | BPZE1 (10 ⁷ or 10 ⁹ CFU) by VaxINator | Assumed Proportion of Subjects Attaining Seroconversion (Placebo) | Proportion of Subjects Attaining Seroconversion (BPZE1) | Minimum Detectable Difference (Treatment – Placebo) |
|----------------------|---|---|---|---|
| N=15 | N=15 | 0.00 | 0.41 | 0.41 |
| | | 0.01 | 0.43 | 0.42 |
| | | 0.05 | 0.54 | 0.49 |
| | | 0.10 | 0.63 | 0.53 |
| | | 0.20 | 0.76 | 0.56 |

N=Sample Size

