4.4.3. Method of Assigning Subjects to Treatment Groups (Randomization)

Enrollment/randomization will be performed through the enrollment module in the electronic data capture system, maintained by the SDCC. Eligible subjects will be randomized and assigned in a 3:3:3:1 ratio to BPZE1 10^7 CFU administered via VaxINator: BPZE1 10^9 CFU administered via VaxINator: placebo

administered via VaxINator: BPZE1 10^9 CFU administered via Needleless Tuberculin Syringe. The randomization is based on a block scheme to provide an approximately balanced allocation to the treatment groups during the study.

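### SAP 8.1 plans no baseline-adjusted analysis of antibody titre and no between-arm GMT or GMFR estimate; a dose effect would be read from an unadjusted 2-fold cut and by eye across columns

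*SAP*

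**What the plan says.** SAP 8.1 lists three serum summaries for each antigen and isotype. The first is "Analyses will include the Geometric Mean Titers (GMTs) along with corresponding 95% confidence intervals"; the same sentence goes on to GMFR and to seroconversion, both taken relative to the Day 1 titre. Seroconversion rates are compared by Barnard's exact test. In the shells (Table 21 onward) the difference, its CI and the p-value belong to the 2-fold rise only, for each VaxINator dose against placebo. GMT and GMFR have no between-arm contrast, and no shell estimates 10^9 against 10^7. The mucosal ratio is handled the same way.

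SAP 6.4 (Covariates and Subgroups) names no covariate. On allocation, SAP 4.4.3 says: "The randomization is based on a block scheme to provide an approximately balanced allocation to the treatment groups during the study"; it mentions no baseline stratum. Protocol 11.4 says the results will inform the Phase 2b dose.

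The documents do link baseline antibody to response. Protocol 2.1.2 reports of Phase 1b: "Additionally, subjects with high baseline antibodies were capable of further seropositive antibody boosting, but at a lower rate and lower percent increase from baseline". A small non-randomised group with "pre-existing high antibody titers for pertactin had a 33% rate of BPZE1 colonization" is set against more than 80% across the randomised groups. Protocol 5.2 now excludes PRN IgG of 125 IU/mL or more. Protocol 5.3.5 says that people screened out at 20 IU/mL under version 3.0 "may be rescreened per the revised exclusion criterion of protocol version 4.0".

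**The concern.** With 15 per arm, Day 1 titres will differ between arms by chance. An arm that starts higher tends to end higher in GMT, and may show a smaller fold rise and fewer 2-fold responders. The two titre summaries can therefore err in opposite directions, and the SAP gives no estimate that settles which to believe. Since it also gives no titre contrast between the two doses, whoever chooses the Phase 2b dose would compare per-arm columns by eye. The Day 1 titre that would sharpen that comparison is already collected on everyone.

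**Working it through.** **1. The plan's own figures.** Table 4 (Protocol 11.2) gives "minimum detectable differences with 80% power" for 15 v 15, using a two-sided Fisher's exact test at alpha 0.05. Exact enumeration at its five rows gives power between 79% and 81%, so Table 4 reproduces. Its detectable differences are 41 to 56 percentage points. Neither document gives a titre SD, a baseline-to-post correlation or a figure for imbalance, so these are assumptions below.

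Table 4 covers dose against placebo only. The same calculation for 10^7 v 10^9 shows that a 50% rate must rise to about 97% for 80% power. From 60% upward, no rate reaches 80% power. The 2-fold cut therefore says little about one dose against the other.

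**2. Size of a chance imbalance.** The SE of the baseline difference between two arms is SD x sqrt(2/15) = 0.365 SD, with a 95% range of +/-0.72 SD. P(|difference| >= 0.5 SD) = 17% per antigen and pair of arms. If the log10 baseline SD is 0.3 to 0.6 (assumption), a chance baseline GMT ratio of 1.5-fold or more has probability 11% to 42%.

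**3. What the imbalance leaves behind.** With slope b of post-dose on baseline log titre and imbalance d, the GMT contrast carries b*d and the GMFR contrast (b-1)*d. Illustration: log10 SD 0.4, d of one SE (0.365 x 0.4 = 0.146, a 1.40-fold baseline ratio) and b = 0.5. The GMT ratio is then off by 10^0.073 = 1.18 and the GMFR ratio by 10^-0.073 = 0.85, in opposite directions, with no vaccine effect at all.

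**4. Precision.** Let r be the baseline-to-post correlation and k the post-dose SD divided by the baseline SD, so b = rk. With baseline variance 1, the contrast variances are proportional to k^2 (GMT), k^2 + 1 - 2rk (GMFR) and k^2(1 - r^2) (ANCOVA, ignoring the small loss from estimating the slope). At k = 1, ANCOVA/GMFR = (1 + r)/2. At k = 2 it is 4(1 - r^2)/(5 - 4r).

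| r | ANCOVA/GMT (any k) | ANCOVA/GMFR, k = 1 | ANCOVA/GMFR, k = 2 |
|---|---|---|---|
| 0.3 | 0.91 | 0.65 | 0.96 |
| 0.5 | 0.75 | 0.75 | 1.00 |
| 0.7 | 0.51 | 0.85 | 0.93 |

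At k = 2 and r = 0.5 the slope is exactly 1, so GMFR is already the right adjustment.

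**5. Validity given the imbalance seen.** These are 200,000 simulated null trials of 15 v 15 with equal SDs, applying a nominal 5% test to each contrast. Over all trials, every method rejects about 5% of the time. Among trials with a baseline difference of 0.5 SD or more:

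| r | GMT | GMFR | ANCOVA |
|---|---|---|---|
| 0.5 | 11% | 12% | 5% |
| 0.7 | 18% | 9% | 5% |
| 0.8 | 21% | 8% | 5% |

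**6. Seroconversion.** The PRN limit rose by a factor of 125/20 = 6.25. If 20% to 50% of subjects lie in the 20-125 IU/mL band (assumption), two arms differ by 4 or more such subjects with probability 11% to 20%. Phase 1b reported 66% seropositive in the high-pertactin group and 100% in the randomised 10^9 group. At that contrast, 4 subjects move an arm's rate by 34 x 4/15 = 9 points, far below Table 4's 41 to 56.

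**The case against.** The strongest reply is that the plan already refers to baseline. GMFR and seroconversion are Day 1-relative, Tables 17 to 20 show Day 1 GMTs by arm, and the reverse cumulative curves include a pre-vaccination panel. A reader who infers that titres are analysed with no reference to baseline would be wrong, and an imbalance would be visible. What remains is that seeing it does not correct it, and fixing the slope at 1 corrects it only if the slope is 1.

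The study is also descriptive: Protocol 11.1 disclaims a formal null hypothesis and immunogenicity is secondary. This limits the weight of the point. It does not answer it, because an adjusted ratio with a CI is an estimate, and the SAP already prints unadjusted p-values.

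Three stronger readings are tempting and unsupported:

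- That baseline antibody drives response in this trial. The evidence is a small non-randomised group with no stated titre threshold, and its response definition also required 4 times the detection limit. No effect below 125 IU/mL is shown.
- That the cut-off change biased the arms mid-trial. Protocol 5.3.5 shows only that people had been screened, not that anyone had been randomised. The change concerns PRN IgG alone and distinguishes no arm.
- That adjustment is worth raising 15 per arm to 20 against either summary. This needs k = 1 and r = 0.5; at k = 2 and r = 0.5 the gain over GMFR is nil.

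Two limits on the remedy stand. Weaker boosting at high baseline suggests different slopes in vaccine and placebo arms, which a common-slope model omits. Adjusting each antigen for its own Day 1 value also does not carry pertactin into the PT, FHA or FIM models.

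**Conclusion.** The gap is real and moderate. SAP 8.1 has no covariate-adjusted titre analysis, no between-arm estimate for GMT or GMFR, and no estimate of one dose against the other. Against the unadjusted GMT, adjustment cuts variance by 9% to 49% for r of 0.3 to 0.7. Against GMFR it cuts variance by 15% to 35% if the two SDs are equal, and by 0% to 7% if the post-dose SD is double. The SDs and r are assumptions.

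A reader might infer that the present plan yields false dose effects too often. It does not: overall error stays near 5% for every method, and the distortion is conditional on an imbalance that arises by chance. Nor is there a planned test of 10^9 against 10^7 that could go wrong; the risk lies in informal reading. The wider PRN limit increases the permitted baseline spread for that antigen and does not itself favour any arm. For seroconversion the likely shift is small.

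**What to change.** Add to SAP 8.1, as estimation without formal testing, a linear model of log10 titre on the three VaxINator arms and log10 Day 1 titre, for each antigen and serum isotype at Days 15, 29 and 181. For the log mucosal ratio, use the screening value as covariate at Days 29 and 181. Report adjusted GMT ratios with 95% CIs for each dose v placebo and for 10^9 v 10^7 by VaxINator. Keep GMT, GMFR and seroconversion as they are.

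The cost is SAP text and additional table shells; no new samples or visits are needed. The downsides should be stated in the SAP. The common-slope linear assumption is hard to check with 15 per arm. The output is also large: 4 antigens x 2 isotypes x 3 visits x 3 contrasts = 72 serum ratios plus 4 x 2 x 3 = 24 mucosal ratios, so 96 per analysis population, none adjusted for multiplicity.
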